7. SAMPLE SIZE

7.1. Sample Size Justification and Calculation

The primary endpoint is the correct localization rate (CLR) at the subject level, in subjects with positive PyL PET/CT findings, defined as the percentage of subjects a one-to-one correspondence between localization of at least one lesion identified on ¹⁸F-DCFPyL PET/CT imaging and the composite truth standard. The composite truth standard is defined in Section 5.1.1

The assumed CLR of ¹⁸F-DCFPyL PET/CT imaging is 30%. Based on the varied published experience with ⁶⁸Ga-PSMA PET/CT and a meta-analysis by Perera *et al*³, approximately 76% (95% confidence interval [CI], 66-85%) of PSMA scans are positive in patients with suspected recurrence of prostate cancer following initial therapy. Therefore, in subjects with negative or equivocal findings for prostate cancer on baseline conventional imaging, 60% of subjects are conservatively estimated to have PyL PET/CT positive findings. In consideration of the extent literature for ⁶⁸Ga-PSMA PET and the present study entry criteria, approximately 30% of PSMA PET/CT positive findings may be verified by biopsy/surgery-based histopathology, conventional imaging, or PSA follow-up post-RT.⁴⁻⁷ It is therefore assumed that 30% of the positive PyL results in the study will be confirmed by the composite truth standard. If 60% of the study subjects have positive PyL scans, and 30% of these positive diagnostic scans are confirmed by the composite truth standard, the use of the PyL PET/CT will permit the detection/localization of recurrent prostate cancer in approximately 18% of the underlying target population, versus at most 5% that could be identified by conventional imaging alone.

The sample size estimates are based on the positive likelihood ratio (PLR) of CLR to prevalence.

The PLR is estimated as
$$PLR = \left(\frac{CLR}{1-CLR}\right) / \left(\frac{prevalence}{1-prevalence}\right)$$
.

Conservatively assuming the initial prevalence rate as a population parameter to be 5% by conventional imaging, ^{8,9} ⁴ if a CLR of 30% is realized, the positive likelihood ratio is expected to be 8.1, implying a considerable increase in the clinical value of PyL PET/CT to identify prostate cancer.

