Using a lower bound for the 95% CI for CLR of 20%, the corresponding lower bound for PLR would be 4.75 based on a normal approximation to the Binomial. This will thus require a total of 81 positive PyL scans, which translates to a total of 134 PyL PET/CT scans or evaluable subjects needed. Accounting for a 30% non-evaluable (including loss to follow-up) rate, approximately 192 subjects will need to undergo PyL PET/CT in the study.

During study enrollment, the rate of positive ¹⁸F-DCFPyL PET/CT scans will be calculated periodically to confirm the assumption of 60%. If the observed rate is lower than expected, the sample size may need to be increased.

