8.4. Missing Efficacy Endpoints

Missing values will not be replaced for any endpoint. There should be no missing primary endpoint values for subjects with evaluable PyL scans as assessed by the central readers unless no follow-up standard of truth (SOT) was completed. The subjects will be classified as true positive, false positive, or unevaluable. If a subject undergoes PyL imaging and does not have any follow-up evaluations or if the follow-up assessments are deemed unevaluable by the central readers based on image quality or other reasons, then that subject will be considered as unevaluable.

Exploratory evaluations of the primary endpoint will be performed using multiple imputation methods to examine the impact of missing or unevaluable SOTs for subjects with positive PyL scans as interpreted by the central readers. These methods are described in detail in section 8.5.2.2.

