- Subjects with positive ¹⁸F-DCFPyL PET/CT findings and missing or unevaluable standards of truth (SOTs) will have SOT responses imputed. Imputations of SOT responses will employ a pattern mixture model based multiple imputation method, assuming the data are MAR. The subjects with unevaluable SOTs will have responses imputed along with those subjects with SOT data within similar baseline PSA groupings (< 0.2 ng/mL, 0.2-<0.5 ng/mL, 0.5-< 1 mg/mL, 1-<2 ng/mL, 2-<5 ng/mL and ≥5 ng/mL). SAS PROC MI will be used, and 100 imputations will be performed for each of the three central readers.
- A second sensitivity analysis will impute SOT responses for subjects with positive ¹⁸F-DCFPyL scans with missing/unevaluable SOT data by sampling from subjects with SOT results by method of SOT, including histopathology, Axumin scan, CT and MRI. If a subject has an unevaluable SOT result, then results from subjects with that same SOT will be used as the basis of the imputation pool. For subjects with no SOT, they will have results imputed with results of subjects with biopsy or surgery with histopathology, Axumin, CT and MRI scans separately.
- A tipping point analysis¹¹ will be performed to examine the multiple imputation method described by baseline PSA grouping. A group of delta (δ) values (-0.95, -0.90, ..., -0.10, -0.05) will be used. After the imputed datasets are obtained from the multiple imputation for each central reader's result, the predicted responses will be estimated within each imputed dataset; applying the delta adjustment to the predicted probability of response for those subjects who had missing or unevaluable SOT results by adding δ, then generating random variates following a Bernoulli distribution. This will create a delta adjusted predicted probability within each imputed dataset. For a given delta, the above imputations should produce 100 CLR estimates for each central reader.

The results for all imputation analyses noted above will be combined using SAS PROC MIANALYZE and estimates of CLR and their respective 95% confidence intervals will be reported for each central reader.

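### SAP 8.5.2.2, second imputation analysis: direct donor sampling pooled with PROC MIANALYZE leaves out uncertainty in the donor success rate, so the sensitivity SE for CLR is about 5% too small, and more only if one small pool fills most of the gaps

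*SAP*

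**What the plan says.** SAP 8.5.2.2 plans three imputation analyses for subjects with positive scans whose standard of truth (SOT) is missing or unevaluable.

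- **By baseline PSA group.** The software and number of imputations are stated: "SAS PROC MI will be used, and 100 imputations will be performed for each of the three central readers".
- **By truth-standard method.** Results are imputed "by sampling from subjects with SOT results by method of SOT, including histopathology, Axumin scan, CT and MRI". For a subject with an unevaluable SOT, "results from subjects with that same SOT will be used as the basis of the imputation pool". For subjects with no SOT at all, "they will have results imputed with results of subjects with biopsy or surgery with histopathology, Axumin, CT and MRI scans separately". No parameter draw, bootstrap of the donors or number of imputations is given.
- **Tipping point.** This applies delta shifts from -0.95 to -0.05 to the PSA-group imputation.

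The section closes by pooling all of them: "The results for all imputation analyses noted above will be combined using SAS PROC MIANALYZE". SAP 8.4 presents 8.5.2.2 as the full specification: "These methods are described in detail in section 8.5.2.2".

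**The concern.** PROC MIANALYZE applies Rubin's rules. Their total variance is correct only if each imputed data set also reflects uncertainty about the rate from which the values are drawn. Sampling straight from the observed donors holds that rate at its observed value in every data set. The between-imputation variance then contains the noise of the draws but not the noise of the donor rate, and the interval is too narrow.

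The purpose of this analysis is to show whether a CLR lower bound above 20% survives gaps in the truth standard. An interval that is too narrow makes the result look more robust than the data support. The SAP also divides donors by method, so it matters whether small pools make the shortfall worse.

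**Working it through.** **Plan's own figure.** SAP 7.1 assumes a CLR of 30%: "It is therefore assumed that 30% of the positive PyL results in the study will be confirmed by the composite truth standard". With a lower 95% bound of 20%, the half-width is 0.10:

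n = 1.96² × 0.30 × 0.70 / 0.10² = 80.67, so 81 positive scans.

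Then 80.67 / 0.6 = 134.5 (stated 134), and 134 / 0.7 = 191.4, so 192. The plan's figures are reproduced.

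**Inputs.**
- Evaluable positives: 81 (SAP 7.1).
- Missing: 81 / 0.7 = 115.7, so N = 116 and m = 35. This applies the plan's 30% non-evaluable rate to positive scans, which is an assumption.
- Donors d who fill the gaps: not in the documents. Assumed 81, 40 or 20.
- Imputations: 100 assumed, since none is stated for this analysis.

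**Formulas.** Let v = p(1 − p) = 0.21. With many imputations the pooled estimate weights each donor by 1 + m/d and each other evaluable subject by 1.

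- True variance = v [(81 − d) + d(1 + m/d)²] / N² = v [81 + 2m + m²/d] / N²
- Rubin variance, direct sampling = v/N + vm/N² = v [N + m] / N² = v [81 + 2m] / N²
- Rubin variance, donors bootstrapped first = v [81 + 2m + m²/d] / N²

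Direct sampling therefore loses exactly the term m²/d, and the bootstrap step restores it.

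**Numbers.** 81 + 2m = 151. The reported SE under direct sampling is √(0.21 × 151) / 116 = 0.0485 in every case.

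| Donors filling all 35 gaps | m²/d | True SE | Variance ratio | SE ratio, formula | SE ratio, simulation |
|---|---|---|---|---|---|
| 81 | 15.1 | 0.0509 | 151/166.1 = 0.91 | 0.95 | 0.95 |
| 40 | 30.6 | 0.0532 | 151/181.6 = 0.83 | 0.91 | 0.90 |
| 20 | 61.3 | 0.0576 | 151/212.3 = 0.71 | 0.84 | 0.83 |

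The simulation used 20,000 runs and 100 imputations. It is slightly lower because the sample value of p(1 − p) averages a little below its true value, most of all in small pools.

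**Gaps spread over methods.** With several pools the lost term is the sum of m_k²/d_k. For four equal pools, 4 × 8.75² / 20.25 = 15.1, the same as for one pool of 81. Simulation agrees (SE ratio 0.94 to 0.95). Splitting donors by method does no extra harm when the gaps are shared in proportion to the donors.

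**Interval widths, direct versus bootstrap first (simulated).** 81 donors: 0.189 versus 0.198. 20 donors: 0.188 versus 0.221. The complete-case Wald width at n = 81 is 2 × 1.96 × √(0.21/81) = 0.200. Direct sampling thus gives an interval narrower than the observed data alone, although no information has been added.

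**Few gaps.** With 10 missing and 81 donors the widths are 0.197 and 0.198, so the effect is negligible. With 10 missing and 20 donors the SE ratio is 0.96 to 0.97.

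**The case against.** **The SAP is silent, not wrong.** It never says that the donor rate is held fixed. It calls the set multiple imputation based on a pattern mixture model and cites a standard text on the subject. An approximate Bayesian bootstrap is also a form of sampling from subjects. This stands in part: if the program already resamples the donors, the fault disappears and only the wording needs completing. But the label does not supply the step, and SAP 8.4 points to this section for the detail. A programmer who follows the sentence literally would write a plain hot deck.

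**Small pools.** A reader might infer that division by method makes a large shortfall inevitable. The documents do not support that. Unevaluable subjects draw from their own method's pool, so their gaps are spread, and the shortfall then stays near 5%. The 10% and 16-17% figures need one small pool to fill all 35 gaps. The nearest case in the SAP is the subjects with no SOT, who are filled from each method in turn; 81 donors split evenly over the four named methods would give about 20 each. Neither the pool sizes nor the number of such subjects is stated.

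**Coverage.** A reader might also take simulated coverage of 92.8% (direct sampling, 81 donors) as damage from the imputation. The complete-case Wald interval at n = 81 and CLR 30% already covers only 92.8%. The SE ratio or the interval width isolates the donor effect; coverage does not.

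**Little hangs on it.** SAP 8.4 calls these evaluations exploratory. The PSA-group and tipping-point analyses test the same conclusion, and the tipping point moves the estimate far more than a 5% change in SE would. This stands, and it limits the importance of the point.

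**Conclusion.** The point holds for the text as written: direct donor sampling pooled by Rubin's rules is improper and understates the SE. At CLR 30%, with 81 evaluable and 35 missing, the SE is about 5% too small with one pool or with gaps spread evenly over four. It is about 10% too small if 40 donors fill every gap and 16-17% too small if 20 do. The missing count rests on reading the plan's 30% non-evaluable rate as the missing-SOT fraction among positive scans.

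It would be wrong to infer that the trial's success claim is at risk. SAP 8.5.2.1 bases success on evaluable subjects, with a lower bound above 0.2 for at least two of three readers, and no imputed result enters that rule. This is a minor, easily repaired weakness in one exploratory sensitivity analysis.

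**What to change.** In SAP 8.5.2.2, add to the second imputation analysis: for each imputation and each method's donor pool, draw a bootstrap sample of the donors (same size, with replacement), then sample the imputed results from that bootstrap sample; use 100 imputations per central reader and pool with PROC MIANALYZE. For subjects with no SOT, apply this within each method's pool in turn, as the SAP already intends, and report the number of donors and of subjects filled beside each result.

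A PROC MI logistic model with method as a class variable is not a substitute, because subjects with no SOT have no method value.

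The cost is a sentence or two in the SAP and a few lines of SAS. The sensitivity intervals become slightly wider (0.198 instead of 0.189 with 81 donors). The bootstrap step is not perfect in very small pools: with 10 donors filling 34 gaps its simulated SE ratio is 0.95, against 0.74 for direct sampling.

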8.5.2.3. Subgroup Analyses

The primary endpoint analysis will be performed for the following subgroups:

- Truth standard category: histopathology, correlative imaging, PSA response following locoregional RT
- Truth standard of each correlative imaging method
- Age: $<65, \ge 65$
- Race: White, Black or African American, Other
- Ethnicity: Not Hispanic or Latino, Hispanic or Latino

- Baseline PSA, categorized as < 0.2 ng/mL, 0.2-<0.5 ng/mL, 0.5-<1 ng/mL, 1-<2 ng/mL, 2-<5 ng/mL, ≥5 ng/mL and the same PSA categories by historical therapy modality (prostatectomy alone, prior radiation therapy, both prostatectomy and prior radiation therapy)
- Historical initial therapy modality(ies) for prostate cancer at study entry: surgery (radical prostatectomy), radiation therapy (to the prostate gland), surgery and radiation therapy, prior androgen deprivation therapy (ADT), ADT and radiation therapy
- Baseline Screening imaging modality, categorized as fluciclovine PET/CT, choline PET, NaF PET, Pelvic CT/MRI, Abdomen CT/MRI, Chest CT/MRI, bone scintigraphy
- Study center: the distribution of treated subjects by center will be created at the end of the study. Small centers with five or fewer treated subjects may be combined into one or more centers for analysis.
- Size of largest lesion (long axis) detected on the PyL image by the central imaging readers: 0-<0.5 cm, 0.5-<1.0 cm, ≥1.0 cm
- Maximum standard uptake value (SUVmax) reported for the subject's lesion(s) on the PyL image by the central imaging readers: ≤2, 2-<5, 5-<10, ≥10
- Time of PyL scan following dosing: < 60 minutes, 60-<90 minutes, 90-≤ 120 minutes, > 120 minutes
- Time since discontinuation of ADT until study entry for subjects with prior ADT use

Subgroup analyses will be performed by tabulating the primary endpoint for each subgroup. For the analysis of the endpoint by SUVmax the tabulations will use the SUVmax value adjusted for lesion long axis. This value is the predicted SUVmax from a logistic regression model of CLR (0=No,, 1=Yes) for subjects with a positive PyL scan as assessed by the central reader, including SUVmax and lesion size (long axis as reported by the central reader). This analysis will be used if the lesion size term is significant at an alpha of 0.05. If the lesion size term is not significant the unadjusted SUVmax values will be used as reported by the central reader in the tabulations.

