5.1.1. Primary Endpoint

The primary endpoint of the CLR is evaluated in a subset of Full Analysis Set (FAS) subjects with at least one positive lesion identified by ¹⁸F-DCPyL PET/CT imaging by the local reader and then evaluated against the composite truth standard by three independent, blinded central imaging readers. The CLR at the subject level is defined as the percentage of subjects for whom there is a one-to-one correspondence between localization of at least one lesion identified on ¹⁸F-DCFPyL PET/CT imaging (by central review) and the composite truth standard, which is defined either as:

- 1) evaluable local histopathology result for prostate cancer from surgery or biopsy performed within 60 days following PyL PET/CT, or
- 2) if evaluable histopathology is not available, informative conventional imaging (e.g., ¹⁸F-fluciclovine PET (preferred if was not performed at baseline) or choline PET; targeted MRI or CT; fluciclovine or choline PET) finding(s) of the anatomical correlate to the PyL-suspected lesion(s) within 60 days following PyL PET/CT, before locoregional or systemic treatment in is started, or
- 3) if neither of the above is available or informative, confirmed PSA response (PSA decline by ≥50% from baseline, confirmed within 4 weeks per central lab evaluation) post-RT (no concomitant ADT) that was initiated within 60 days following PyL PET/CT. PSA will be collected every 3 months, up to 9 months until PSA response (if achieved) is confirmed.

The CLR in percent is computed as $100 \times TP/(TP+FP)$; TP = true positives, FP = false positives.

A true positive (TP) result is defined as a subject with both a positive lesion(s) on ¹⁸F-DCFPyL PET/CT evaluated by at least one central reader and a positive result on the composite truth standard in the following order of importance:

- Positive finding for prostate cancer of a PyL-suspected lesion according to local histopathology (confirmed by at least one anatomical correlate will suffice to declare the PyL PET/CT assessed by the central reader defining a true positive), or
- Positive finding for prostate cancer of a PyL-suspected lesion upon follow-up correlative imaging by CT, MRI, whole body bone scan, NaF, fluciclovine or choline PET/CT

performed following PyL PET/CT (one confirmed anatomical correlate will suffice to declare the PyL PET/CT assessed by the central reader a true positive), or

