• PSA decreases by ≥50% from baseline following RT (without concomitant ADT) up to nine months following initiation of such treatment if the other two truth standards were not performed or did not provide evaluable results

False positives will be defined as subjects with positive lesion(s) on PyL PET/CT from at least one central reader who has the following negative findings for prostate cancer according to the composite truth standard:

- Negative finding for prostate cancer of a PyL-suspected lesion according to local histopathology, or
- Negative finding for all PyL positive lesion(s) upon follow-up correlative imaging performed following PyL PET/CT, or
- PSA does not decrease by ≥50% from baseline following RT (without concomitant ADT) up to 9 months following initiation of such treatment.

The CLR lesion location(s) will be matched with the CLR lesion location(s) identified by the composite truth standard to determine if colocalization is successful, denoting a true positive (TP) assessment. If a subject has more than one lesion identified by pathology or by correlative imaging, then at least one lesion must be successfully colocalized for the subject to be considered a TP. The anatomic regions and CLR lesion locations matched by laterality (right or left) where applicable are presented in Table 3. The pelvic lymph nodes are grouped together for analysis in alignment with the data collected in the PyL-2301 (OSPREY) study. Within the prostatic region and extra-pelvic lymph nodes, specific CLR lesion location groupings are further modified specific for PET/CT findings based on Prostate Cancer Molecular Imaging Standardized Evaluation (PROMISE)² intended to guide reproducibility, general applicability and clinical relevance.

Table 3: Lesion Locations and Anatomic Regions

Anatomic Region	CLR Lesion Locations
Prostatic	Prostate gland or prostate bed (including seminal vesicles)
Pelvic Lymph Nodes	 Right Pelvic (including Internal Iliac [Hypogastric], External Iliac, Common Iliac, Obturator) Left Pelvic (including Internal Iliac [Hypogastric], External Iliac, Common Iliac, Obturator) Other pelvic (including Rectal/perirectal and Presacral)

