8.5.2.1. Primary Analysis of Primary Endpoint

The primary endpoint is the CLR at the subject level, defined as the percentage of subjects with positive ¹⁸F-DCFPyL PET/CT imaging from the central reads for whom there is a one-to-one correspondence between the CLR lesion location of at least one lesion identified on ¹⁸F-DCFPyL PET/CT imaging and the composite truth standard, computed as 100×TP/(TP+FP). There are three independent central ¹⁸F-DCFPyL PET/CT readers who will report whether each subject's PET/CT scan is positive or negative and will indicate the location(s) of the lesion(s) for all positive scans. The location(s) of the lesions will be matched with the standard of truth to determine if colocalization is successful, denoting a true positive (TP) assessment. If a subject has more than one lesion identified by pathology or by correlative imaging, then at least one lesion must be successfully colocalized for the subject to be considered a TP. The lesion locations for analysis as well as anatomic regions are defined in Table 3 in section 5.1.1.

PyL images obtained for subjects will be evaluated by three central readers. The results for all subjects will be summarized for each reader. The CLR is computed as TP/(TP+FP) *100% for each reader across all evaluable subjects. The respective two-sided 95% confidence interval for each reader will be computed using the binomial approximation to the normal distribution for each central reader. If the lower bound of the 95% CI is >0.2 for at least two of the three independent imaging reviewers, then the primary endpoint analysis is considered a success.

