8.5.5. Other Efficacy Data

Summaries will be created for the following recorded measurements:

- Pathology results by lesion location and region
- Imaging results by lesion location and anatomic region for the central imaging readers, the imaging truth panel and the local site interpretation
- Lesion sizes by lesion location as recorded by the central imaging readers (and Imaging Truth Panel), excluding lesions indicated as unmeasurable
- SUV_{max}, and SUV_{mean} as recorded by the central imaging readers by lesion location
- The number of lesions detected per subject per CLR lesion location and per region (prostatic, pelvic, extra-pelvic)

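### CLR by lesion size and SUVmax is grouped on the subject's largest or hottest lesion, so lesion number alone can make CLR appear to rise with size or uptake

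*SAP*

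**What the plan says.** SAP 8.5.2.3 plans the primary endpoint by two lesion descriptors, each reduced to one value per subject and reader: "Size of largest lesion (long axis) detected on the PyL image by the central imaging readers", in three groups cut at 0.5 and 1.0 cm, and "Maximum standard uptake value (SUVmax) reported for the subject's lesion(s) on the PyL image by the central imaging readers", in four groups cut at 2, 5 and 10. The resulting displays are tables 14.2.1.3.1 and 14.2.1.4 in the SAP appendix. If lesion size is significant in a logistic model of CLR, SUVmax is to be adjusted for long axis; no other adjustment is planned. The protocol's statistics section does not list these subgroups.

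The outcome is decided where a reader's lesion meets the truth standard. SAP 5.1.1 and 8.5.2.1 say that with more than one truth lesion, "at least one lesion must be successfully colocalized for the subject to be considered a TP". For correlative imaging, "one confirmed anatomical correlate will suffice to declare the PyL PET/CT assessed by the central reader a true positive", while a false positive by negative imaging needs "Negative finding for all PyL positive lesion(s) upon follow-up correlative imaging performed following PyL PET/CT". Matching uses the CLR locations of SAP Table 3, where the internal, external and common iliac and obturator nodes on one side form one location.

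SAP 8.5.5 summarises lesion number, size and SUV (the last "as recorded by the central imaging readers by lesion location"), but links none of them to true or false positive status. Lesion number is not a subgroup, stratum or covariate for CLR.

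**The concern.** The row of the table and the outcome share a cause. The maximum over a subject's lesions rises with the number of lesions. So does the chance that at least one is confirmed, if several are checked. The row label may also belong to a lesion other than the one biopsied or correlated.

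The likely use of such tables is to judge how far a small or faint PyL finding can be relied on. A gradient produced by lesion number could be taken for a property of uptake or size.

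**Working it through.** **The plan's own figure.** With CLR 30% and a lower 95% bound of 20%, n = 1.96² × 0.30 × 0.70 / 0.10² = 80.67, rounded up to 81 positive scans, as SAP 7.1 states. It is used below only for cell sizes.

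**Inputs.** From the SAP: the any-match rule, one maximum per subject, and the cut-points. Assumed, because the documents do not give them: 1/2/3/4/5 lesions in 50/20/15/10/5% of subjects; each lesion confirmed with probability q = 22%, whatever its SUV; lesion SUV log-normal with median 5 and log-SD 0.8. Each lesion counts as a separate chance of a match.

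**Step 1, outcome against lesion number.** If k independent lesions are checked, P(TP) = 1 − (1 − q)^k. With q = 22% and k = 1 to 5 this is 22.0, 39.2, 52.5, 63.0 and 71.1%. Weighted by the assumed mix, overall CLR is 36.6%.

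**Step 2, lesion number against the row.** In a simulation of 400,000 subjects, mean lesions per subject across the four maximum-SUV groups are 1.06, 1.41, 2.08 and 2.57.

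**Step 3, CLR by maximum SUVmax, with no true SUV effect.**

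| Setting | ≤2 | 2 to <5 | 5 to <10 | ≥10 | Spread (points) |
|---|---|---|---|---|---|
| Independent lesions | 22.9 | 28.6 | 38.0 | 44.1 | 21 |
| SUV correlation within subject 0.5 | 26.3 | 32.1 | 37.9 | 42.2 | 16 |
| SUV correlation 0.9 | 32.4 | 35.1 | 37.2 | 39.4 | 7 |
| Confirmation correlation (latent) 0.5 | 22.6 | 26.5 | 32.3 | 36.4 | 14 |
| Confirmation correlation 0.8 | 22.4 | 24.7 | 28.0 | 30.8 | 8 |
| 25% of subjects judged on one lesion | 22.5 | 26.9 | 33.9 | 38.7 | 16 |
| Both correlations 0.5, 25% judged on one lesion | 24.0 | 27.1 | 29.8 | 32.0 | 8 |
| All judged on one randomly chosen lesion | 22.1 | 22.0 | 22.3 | 22.2 | 0 |

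With independent lesions, changing the log-SD to 0.6 or 1.0 gives a spread of 23 or 20 points.

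**Step 4, is lesion number the cause?** In the independent case, CLR among one-lesion subjects is flat at 22% across the groups. So is the confirmation rate when each lesion is grouped by its own SUV.

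**Step 5, size and the planned adjustment.** With a different assumed mix (1/2/3/4 lesions in 50/25/15/10%, q = 20%, size log-normal with median 0.8 cm and log-SD 0.6, unrelated to truth), CLR by largest lesion is 22.0, 29.0 and 36.7% across the three size groups. Largest size carries the same lesion-number effect, so adjusting SUVmax for long axis does not remove it.

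**The case against.** **Size.** A reader might infer from the independent-lesion case that the tables will show a strong false gradient. The documents do not support that: they give no lesion counts, SUV distribution or per-lesion confirmation rate, and every other setting that was varied for correlation or truth route gives 16 points or less. Matching by grouped location points the same way, because several nodes in one group give one location match. This objection stands.

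**Truth routes.** The effect needs a source that can check several lesions, meaning correlative imaging or surgery. A biopsy of one lesion, if not chosen for its size or uptake, gives no false gradient. PSA response has no location match in SAP Table 4. CLR by truth-standard category is planned, but it is not crossed with size or SUV. The objection limits the effect without removing it.

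**Precision.** In the independent case the four SUV groups hold 6.6, 26.1, 34.5 and 32.8% of subjects, or about 5, 21, 28 and 27 of 81. At n = 21 and CLR 29% the half-width is 1.96 × √(0.29 × 0.71 / 21) = 19 points. The artefact is about the size of sampling noise in one trial. This lowers the priority, though a systematic pattern can still mislead.

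**Subject-level descriptors.** The endpoint is subject-level, the SAP states no lesion-level purpose for these tables, and no claim depends on them. That is correct, and the concern is about how they will be read. The hottest-lesion reading of the SUV item is natural, and the title of table 14.2.1.4 supports it, but the SAP does not spell it out. The largest-lesion wording is explicit.

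**Conclusion.** The point holds as a limitation of two descriptive tables. As specified, they can show CLR rising with lesion size or SUVmax when neither predicts confirmation, and nothing in the SAP separates that from a real relation. Under the assumed inputs the spread from lowest to highest SUV group is about 21 points with independent lesions, about 7 to 16 with within-subject correlation or some subjects judged on one lesion, and zero if every subject is judged on one. These figures are illustrative; the trial's own lesion counts would settle the size.

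A reader might also infer that the primary result is distorted. It is not: the overall CLR, the two-of-three-readers success rule and the sample size do not use these groupings. Severity: consider.

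**What to change.** In tables 14.2.1.3.1 and 14.2.1.4:

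- (a) Present subject-level CLR by size and SUVmax separately for subjects with one and with more than one PyL-positive CLR location for that reader.
- (b) For subjects with histopathology or correlative imaging, add a tabulation by CLR location assessed by the truth standard. Use the largest long axis and highest SUVmax that the reader recorded in that location, include confirmed and unconfirmed locations alike, and give a CI that allows for clustering within subject.

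Part (a) alone is not complete. If each lesion sits in its own location, the independent case is flat at 22% in the one-location stratum, but still runs 45, 51 and 54% over the upper three SUV groups in the other stratum, because that stratum mixes two to five lesions. Part (b) addresses this. Its level is a per-location rate (22% in this example), so it should not be set against the subject-level CLR (36.6%).

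The cost is SAP wording and programming on data already recorded by location. Cells become smaller, PSA-response subjects leave tabulation (b), and several nodes grouped in one location cannot be told apart.
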